#### **5.8.2.5. Time to and Duration of HI-E Response**

Time to and duration of HI-E response will be analyzed for HI-E responders only.

Time to HI-E response will be defined as the time from the first dose date to the first date of any rolling 8-week interval achieving HI-E response.

Duration of HI-E response will be defined as below for LTB and HTB patients, respectively:

- For LTB patients, duration of HI-E response will be calculated as the longest interval during which all hemoglobin measurements have an increase of  $\geq 1.5$  g/dL from baseline.
- For HTB patients, duration of HI-E response will be calculated for the longest such interval as the time from the start date of the first rolling 8-week interval achieving hematologic response to the end date of the last consecutive rolling 8-week interval achieving response.

When there are multiple disjoint intervals with response, the longest interval will be used. Patients with response ongoing by the analysis cutoff day will be censored at that date.

Both time to and duration of HI-E response will be analyzed as continuous variables and summarized by descriptive statistics. In addition, duration of HI-E response will also be analyzed as a time to event endpoint. The survival curves will be estimated using Kaplan-Meier method if the number of patients is more than 5.

HI-E responders may experience multiple periods of  $\geq 8$  weeks of HI-E response. For all HI-E responders, the number of episodes and cumulative duration will be summarized. As an exploratory analysis, the cumulative duration of the multiple responses will be analyzed using Kaplan-Meier method.

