15.2.3. Secondary Analysis

Efficacy/Pharmacodynamic Effects Analysis of Secondary Endpoints:

All efficacy analyses will be performed for the EE and mITT populations.

Efficacy will be evaluated by determining the proportion of patients who have a modified HI-E erythroid response rate based upon the IWG 2006 criteria ([Appendix 5](#)), defined as 1) A mean hemoglobin increase ≥ 1.5 g/dL over an 8-week period as compared to baseline, not influenced by RBC transfusion in NTD patients or 2) A decrease of ≥ 4 units or $\geq 50\%$ of units of RBCs transfused over a period of 8 weeks, relative to the number of units of RBCs transfused in the 8 weeks immediately prior to Cycle 1 Day 1 in TD patients.

Baseline hemoglobin will be the average of two or more measures (not influenced by RBC transfusion) performed during the screening period for study A536-03 (for patients without interruption) or study A536-05 (for patients with interruption).

Baseline units of RBCs transfused will be the 8-week period prior to study A536-03 (for patients without interruption) or study A536-05 (for patients with interruption).

The erythroid response will be summarized using both a point estimate and its exact 95% confidence interval based on binomial distribution.

No direct comparison testing with concurrent or historical controls will be performed.

Analysis of other secondary efficacy/pharmacodynamic endpoints will include:

- Time to HI-E response and duration of HI-E response as per the IWG 2006 criteria and modified IWG criteria.
- Mean RBC transfusion burden
- Rate of RBC transfusion-free period lasting \geq 8 weeks in TD patients.
- Mean hemoglobin level change in NTD patients
- Other PD endpoints including:
 - Biomarkers for iron overload/metabolism
 - Relationship of biomarkers to response
 - Rates of HI-E, HI-N and HI-P

Exploratory endpoints will include:

- Biomarkers related to the TGF β superfamily.
- Patient-reported quality of life using tools including but not limited to the FACT-An questionnaire.

All binary endpoints will be summarized using both a point estimate and its exact confidence interval based on the binomial distribution. The time-to-event type secondary endpoints will be analyzed using Kaplan-Meier method to estimate the survival curve and median time to event and 95% confidence interval.

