#### 5.8.2.2. RBC Transfusion Independence

For patients with  $\geq 2$  units of RBC transfusion at baseline, RBC transfusion independence (RBC-TI) response is defined as not requiring RBC transfusion for 8 or more weeks while on treatment.

The proportion of RBC-TI responders will be estimated by a point estimate along with the exact 95% confidence interval based on binomial distribution. The denominator is the number of patients with  $\geq 2$  units of RBC transfusion at baseline.

Time to RBC-TI will be defined as the time from the first dose date to the starting date of the first consecutive 8-week interval not requiring RBC transfusion. Duration of RBC-TI will be calculated as the longest period of time not requiring RBC transfusion during treatment and will be censored at the analysis cutoff date for ongoing responses.

Both time to and duration of RBC-TI will be analyzed as continuous variables and summarized by descriptive statistics for RBC-TI responders only. Duration of RBC-TI will also be analyzed as a time to event variable using Kaplan-Meier method.

The derivations of RBC-TI response, time to and duration of RBC-TI will be listed for each patient.

RBC-TI responders may experience multiple periods of  $\geq 8$  weeks of RBC-TI response. For all RBC-TI responders, the number of episodes and cumulative duration will be summarized. As an exploratory analysis, the cumulative duration of the multiple responses will be analyzed using Kaplan-Meier method.

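### Time to HI-E response is summarised in responders only, an undeclared change from the protocol's Kaplan-Meier analysis; the SAP's added time to RBC-TI has the same limitation but is not a departure

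*SAP*

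**What the plan says.** **Protocol.** Section 15.2.3 lists among the secondary analyses "Time to HI-E response and duration of HI-E response as per the IWG 2006 criteria", and also under the modified criteria. On population it says: "All efficacy analyses will be performed for the EE and mITT populations". On method it says: "The time-to-event type secondary endpoints will be analyzed using Kaplan-Meier method to estimate the survival curve and median time to event", with a 95% confidence interval. For transfusion independence it lists only a proportion ("Rate of RBC transfusion-free period lasting" at least 8 weeks in TD patients) and no time to reach it. Section 15.5 requires departures from the protocol's analyses to be flagged in the SAP.

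**SAP, time to HI-E (5.8.2.5).** "Time to and duration of HI-E response will be analyzed for HI-E responders only". Then: "Both time to and duration of HI-E response will be analyzed as continuous variables and summarized by descriptive statistics". Kaplan-Meier returns for one of the two quantities: "In addition, duration of HI-E response will also be analyzed as a time to event endpoint".

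**SAP, time to RBC-TI (5.8.2.2).** Time and duration are treated as continuous and "summarized by descriptive statistics for RBC-TI responders only". Here too, Kaplan-Meier is added for duration alone.

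**SAP, change table (5.13).** It has five entries: the LTB/HTB terminology, ITT in place of mITT, no analysis of the modified-HI-E times, no EE analysis, and the baseline hemoglobin definition. The new population and method for time to standard HI-E are not among them.

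**The concern.** Time to first response is an ordinary time-to-event quantity. Some patients never respond, and some stop treatment before they could. Restricting the summary to those who did respond selects on a later outcome. The median then describes speed among responders. It does not say how soon a patient starting treatment can expect a response, and it tends to be read as if it did.

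Two things are at stake. The first is interpretation of a named secondary endpoint: a responders-only median will look faster than the all-patient median, most of all when few respond. The second is traceability. The protocol's population and method were both replaced, and the table meant to record such changes is silent. Because SAP 5.13 drops the modified-criteria times, the standard-criteria analysis is the only time-to-HI-E result left.

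**Working it through.** The documents state no response rate and no time to response, so there is no plan figure to reproduce. The check has a textual part and an illustrative part.

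**1. Texts side by side**

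| | Protocol 15.2.3 | SAP | Declared in SAP 5.13? |
|---|---|---|---|
| Time to standard HI-E: population | EE and mITT | HI-E responders (5.8.2.5) | Only the EE and mITT-to-ITT changes |
| Time to standard HI-E: method | Kaplan-Meier, median, 95% CI | Descriptive statistics (5.8.2.5) | No |
| Time to RBC-TI | Not an endpoint | Descriptive, responders (5.8.2.2) | Not a departure |

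After the declared changes, the expected analysis of time to HI-E would be Kaplan-Meier in the ITT population. SAP 5.8 itself assigns all efficacy analyses to ITT. SAP 5.2 has a general rule for presenting Kaplan-Meier curves for time-to-event variables, but 5.8.2.5 gives that label to duration only, so the rule does not clearly bring the curve back for time to response.

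**2. Why the two medians differ**

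Let F(t) be the proportion of all patients who have responded by time t, rising to p, with complete follow-up. The all-patient median is where F reaches 0.5. The responders-only median is where F reaches p/2. Since p/2 < 0.5 whenever p < 1, the second comes first.

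**3. Illustration with never-responders, closed form**

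Assumed: times among eventual responders are exponential with mean 12 weeks, and there are no competing events.

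- Responders-only median: 12 × ln 2 = 8.3, about 8 weeks.
- All-patient median: −12 × ln(1 − 0.5/p), for p > 0.5.
- p = 0.6: −12 × ln(0.1667) = 21.5 weeks.
- p = 0.7: −12 × ln(0.2857) = 15.0 weeks.
- p ≤ 0.5: not reached.

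Both medians scale with the assumed mean, so their ratio does not depend on it: 21.5/8.3 = 2.6 at 60% and 15.0/8.3 = 1.8 at 70%.

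**4. Illustration with never-responders, simulated**

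Assumed: median 2 months in those who can respond, N = 153 (the stated maximum), 60 months of follow-up, 1000 runs per setting. All-patient values are Kaplan-Meier medians with non-responders censored. NR = not reached.

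| Response rate | 20% | 40% | 60% | 80% | 95% |
|---|---|---|---|---|---|
| Responders only, no dropout (months) | 2.0 | 2.0 | 2.0 | 2.0 | 2.0 |
| All patients, no dropout | NR | NR | 5.2 | 2.8 | 2.2 |
| Responders only, median 18 months on treatment | 1.8 | 1.8 | 1.8 | 1.8 | 1.8 |
| All patients, median 18 months on treatment | NR | NR | 5.1 | 2.8 | 2.2 |

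N = 75 gives nearly the same values.

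**5. Illustration without never-responders**

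Assumed: constant hazard λ = −ln(1 − p)/F, with follow-up F of 12 or 60 months. Responders-only median = −ln(1 − p/2)/λ; all-patient median = ln 2/λ, if within F. Example, F = 12 and p = 0.6: λ = 0.916/12 = 0.0764, giving 0.357/0.0764 = 4.7 and 0.693/0.0764 = 9.1 months.

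| Response rate | 20% | 40% | 60% | 80% | 95% |
|---|---|---|---|---|---|
| F = 12, responders only (months) | 5.7 | 5.2 | 4.7 | 3.8 | 2.6 |
| F = 12, all patients | NR | NR | 9.1 | 5.2 | 2.8 |
| F = 60, responders only | 28.3 | 26.2 | 23.4 | 19.0 | 12.9 |
| F = 60, all patients | NR | NR | 45.4 | 25.8 | 13.9 |

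In every setting the responders-only median is the lower one, and the gap is widest at low response rates.

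**The case against.** The strongest reply is that little is hidden. The summary is openly labelled as responders only. Non-responders remain in the denominator of the HI-E rate, which SAP 5.8.2.3 reports with an exact 95% CI. RBC-TI is handled likewise in 5.8.2.2, with a stated denominator, and the SAP provides patient listings. If stopping treatment is a competing event and nobody is censored before response, cumulative incidence is simply the response proportion multiplied by the responders' time distribution, so it could be rebuilt. The endpoint is also secondary and descriptive, in a single-arm extension whose primary objective is safety, with no hypothesis test. All of this stands, and it limits the importance of the point. It does not supply the protocol's curve or its interval, and a mean, median and range do not give the full time distribution. That SAP 5.13 is headed as covering major changes does not help either: it records a pure relabelling but omits a new population and method for a named endpoint.

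Two stronger readings are tempting, and the documents do not support them.

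- A reader might infer that time to RBC-TI is also an undeclared departure. It is not. The protocol lists only a rate for transfusion independence, and the time was added in the SAP.
- A reader might infer that the responders-only median is the same short time whatever the response rate. That constancy is built into models with a never-responder fraction and timing unrelated to p (steps 3 and 4). In step 5 the median moves, for example from 28.3 to 12.9 months. No document figure supports calling it short.

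**Conclusion.** The point holds for time to standard HI-E. The SAP replaced an all-patient Kaplan-Meier analysis with a responders-only descriptive summary and did not record the change where Protocol 15.5 requires it. For time to RBC-TI only the conditioning limitation applies.

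On size, the direction is firm: the responders-only median was below the all-patient median in every scenario. The amount is illustrative, because response rates and time distributions are assumed. With never-responders, the all-patient median is about 2.6 times the responders-only one at 60% response, about 1.8 times at 70%, and not reached at 50% or below. At 95% response the gap is small (2.2 against 2.0 months in step 4). The illustrations ignore competing events, so they do not predict a cumulative-incidence result.

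No error rate or formal decision depends on this. It is a low-cost improvement to a secondary, descriptive endpoint, not a threat to the study's primary purpose.

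**What to change.** 1. Estimate time to first HI-E in all ITT patients, and time to RBC-TI in all patients with at least 2 units at baseline. Use one or both of two estimators, keeping their rules separate:
   - Kaplan-Meier, the protocol's method for HI-E, with median and 95% CI. Every patient without a response is censored at the SAP 5.8 analysis cutoff day. Because that day is tied to the last dose, this treats patients who stopped as if they had the same later prospects as those who continued; the SAP should say so.
   - Cumulative incidence. Death or treatment discontinuation before response is a competing event, and only patients with neither a response nor a competing event are censored at the cutoff day.
2. Keep the responders-only summaries in 5.8.2.2 and 5.8.2.5 as supplements, labelled as conditional on response.
3. Add an entry to SAP 5.13 for time to HI-E stating what differs from Protocol 15.2.3. If cumulative incidence replaces Kaplan-Meier, or the responders-only summary stays as the sole analysis, that is itself a departure to record. No such entry is needed for time to RBC-TI as a departure, though noting it as an added endpoint would be helpful.

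The cost is one more table or figure per endpoint from derivations the SAP already specifies. The reported times will be longer, and a median may not be reached.

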9.2. Selection of Study Population

9.2.1. Inclusion Criteria

All patients must meet the following criteria:

1. Completion of the treatment period in the base study A536-03.
2. Females of child bearing potential (defined as sexually mature women who have not undergone hysterectomy or bilateral oophorectomy, or are not naturally postmenopausal ≥ 24 consecutive months) must have negative urine or blood pregnancy test prior to enrollment and use adequate birth control methods (abstinence, oral contraceptives, barrier method with spermicide, or surgical sterilization) during study participation and for 12 weeks following the last dose of ACE-536. Males must agree to use a latex condom during any sexual contact with females of child-bearing potential while participating in the study and for 12 weeks following the last dose of ACE-536, even if he has undergone a successful vasectomy. Patients must be counseled concerning measures to be used to prevent pregnancy and potential toxicities prior to dosing with ACE-536.
3. Patient is able to adhere to the study visit schedule, understand and comply with all protocol requirements.
4. Patient understands and is able to provide written informed consent.

Patients with treatment interruption (defined as patients who completed the A536-03 EOS visit) must also meet the following criteria:

5. Documented diagnosis of idiopathic/de novo MDS or non-proliferative chronic myelomonocytic leukemia (CMML) according to WHO criteria¹⁶ (white blood count [WBC] $< 13,000/\mu\text{L}$) that meets International Prognostic Scoring System (IPSS) classification ([Appendix 2](#)) of low or intermediate-1 risk disease as determined by microscopic and standard cytogenetic analyses of the bone marrow and peripheral complete blood count (CBC) obtained during screening;
6. Anemia defined as:

- Mean hemoglobin concentration < 10.0 g/dL of 2 measurements (one performed within one day prior to Cycle 1 Day 1 and the other performed 7-28 days prior to Cycle 1 Day 1) for NTD patients (defined as having received < 4 units of RBCs within 8 weeks prior to Cycle 1 Day 1), OR
- Transfusion Dependent (TD), defined as having received \geq 4 units of RBCs within 8 weeks prior to Cycle 1 Day 1.

7. Platelet count ($\geq 30 \times 10^9/L$).
8. ECOG performance status of 0, 1, or 2 (if related to anemia).

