10.8. Individual Dose Modification Rules

The following dose modification rules include parameters which may indicate when a dose delay and/or dose reduction is required. These rules should be assessed prior to each dosing. If a dose delay is required the patient should have visits every 1-3 weeks to assess hematology results and AEs until the patient is eligible to receive the next dose of ACE-536.

Observation on Dosing Day	Action	ACE-536 Dose Modification
Hemoglobin \geq 12 g/dL	Hold dose and monitor patient until hemoglobin $<$ 11 g/dL	Resume dosing once hemoglobin $<$ 11 g/dL
Hemoglobin \geq 2 g/dL increase from the previous dosing day, not attributable to RBC transfusion	Continue dosing	Reduce the dose by 1 dose level
Non-hematologic AE \geq Grade 3, at least possibly related to study drug	Hold dose and monitor patient until resolution of AE to \leq Grade 1 or baseline	Resume dosing upon resolution of the AE to \leq Grade 1 or baseline, and reduce the dose by 1 dose level ^a
\geq 50% increase in white blood cell count (WBC) compared to pre-dose WBC of previous treatment cycle and above upper limit of normal in the absence of an associated condition (e.g., infection or concomitant corticosteroid use) ^b	Dose delay; recheck CBC, including WBC at least weekly during dose delay.	Treatment may be resumed if WBC values are below upper limit of normal within 2 weeks
	If WBC remains above upper limit of normal for \geq 2 consecutive weeks in absence of an associated condition (eg, infection or concomitant corticosteroid use); continue dose delay and collect bone marrow/peripheral blood samples to assess MDS disease status.	Treatment may be resumed if: 
 Absence of disease progression per IWG response criteria for altering natural history of MDS¹ AND 
 WBC values return below upper limit of normal Discontinue treatment if: 
 Disease progression per IWG response criteria for altering natural history of MDS¹ OR 
 WBC remain above upper limit of normal
Presence of \geq 1% blasts in peripheral blood (based on local laboratory hematology sample)	Dose interruption; immediately prepare peripheral blood smear for cytomorphology assessment.	If cytomorphology assessment confirms \geq 1% blasts in the peripheral blood; discontinue treatment If cytomorphology assessment determines $<$ 1% peripheral blasts

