10.10. Other Considerations for Dose Modification, Delay or Discontinuation

For individual patients judged by the investigator to be at an unacceptable risk, but who do not meet the protocol-defined conditions for a dose modification or interruption, the investigator should consult with the medical monitor to decide whether to continue dosing at the same dose level, reduce the dose level, delay the patient's dose, or discontinue the patient's treatment with ACE-536.

Patient treatment interruption for site administrative reasons will be allowed between Cycles 17 and 18 and between Cycles 35 and 36 upon discussion with the sponsor.

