#### 5.8.2.3. HI-E Response Rate

Erythroid (HI-E) response will be defined following IWG 2006 criteria.

- For low transfusion burden (LTB) patients, a hemoglobin increase of  $\geq 1.5$  g/dL from baseline during any rolling 8-week period in the absence of transfusion. The rolling 8-week period starts and ends at a hemoglobin measurement date with duration  $\geq 8$  weeks.

- For high transfusion burden (HTB) patients, a reduction by  $\geq 4$  RBC units transfused during any rolling 8-week interval on treatment compared to baseline.

A point estimate of the proportion of HI-E responders will be presented along with its associated exact 95% confidence interval based on binomial distribution. HI-E response will also be listed for each patient.

There are two versions of a HI-E response for LTB patients.

- All hemoglobin values increase of  $\geq 1.5$  g/dL from baseline during any rolling 8-week period in the absence of transfusion.
- Mean hemoglobin value increase of  $\geq 1.5$  g/dL from baseline during any rolling 8-week period in the absence of transfusion.

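### For LTB patients with baseline hemoglobin of 9.5 g/dL or more, a completed protocol hold at 12 g/dL always ends the recorded HI-E interval, and the SAP does not say how holds are handled

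*SAP*

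**What the plan says.** - **Duration rule (SAP 5.8.2.5).** For LTB patients (the protocol's NTD patients), "duration of HI-E response will be calculated as the longest interval during which all hemoglobin measurements have an increase of" at least 1.5 g/dL over baseline. If there are several separate intervals, the longest is used. Only a response still ongoing at the analysis cutoff day is censored. The number of episodes and the cumulative duration are also summarized, with an exploratory Kaplan-Meier analysis of cumulative duration.
- **Dose hold (Protocol 10.8).** When hemoglobin is 12 g/dL or more on a dosing day, the action is "Hold dose and monitor patient until hemoglobin $<$ 11 g/dL"; dosing resumes once that is met. This row names no dose reduction. On monitoring: "If a dose delay is required the patient should have visits every 1-3 weeks to assess hematology results and AEs".
- **Baseline range (Protocol 9.2.1).** NTD patients with treatment interruption need "Mean hemoglobin concentration < 10.0 g/dL of 2 measurements". Patients without interruption keep their A536-03 baseline (SAP 5.1), and the A536-03 hemoglobin entry limit is not given. Protocol Appendix 5 applies HI-E to pretreatment hemoglobin below 11 g/dL.
- **Excluded values (SAP 5.8).** The only hemoglobin exclusion stated for the efficacy derivations covers the 7 days after an RBC transfusion. Dose holds are not mentioned.
- **Dropped endpoint (SAP 5.13).** Time to and duration of modified HI-E will not be analyzed, so the rule above is the only LTB response-duration definition left.

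**The concern.** A hold is a planned reaction to a high hemoglobin. While drug is withheld, hemoglobin is meant to fall, and dosing restarts only after it has fallen. The duration rule reads the same fall as loss of response. In patients for whom the restart level lies below the response threshold, the recorded duration then reflects when hemoglobin first reached 12 g/dL and how quickly it fell on hold, not how long the drug would keep working.

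The study gives up to 60 months of treatment, and durability of response is one of the things that readers will take from it. A short LTB duration could be read as waning effect when it only marks the first hold.

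**Working it through.** The plan states no figure for this endpoint, so there is none to reproduce. The check has three parts.

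**1. Threshold arithmetic (exact, from the documents)**

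Inputs: response threshold T = B + 1.5, where B is baseline (SAP 5.8.2.5); hold at 12 or more, release below 11 (Protocol 10.8).

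A release value is certain to be a non-response value when T is 11 or more: B + 1.5 ≥ 11, so B ≥ 9.5. Below that, hemoglobin can fall 11 − T = 9.5 − B below the release level before response is lost.

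| B (g/dL) | T = B + 1.5 | Room below 11 (9.5 − B) | Rise at the trigger (12 − B) | Rise left at 11 (11 − B) |
|---|---|---|---|---|
| 9.9 | 11.4 | none (−0.4) | 2.1 | 1.1 |
| 9.75 | 11.25 | none (−0.25) | 2.25 | 1.25 |
| 9.5 | 11.0 | none (0) | 2.5 | 1.5 |
| 9.0 | 10.5 | 0.5 | 3.0 | 2.0 |
| 8.5 | 10.0 | 1.0 | 3.5 | 2.5 |
| 7.5 | 9.0 | 2.0 | 4.5 | 3.5 |

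At B = 9.5 the release value must be strictly below 11.0, so the rise is strictly below 1.5. Release requires such a value to be measured, so a completed hold leaves at least one non-response value in the data.

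**2. What the SAP does with that value**

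It is not excluded, because the exclusion concerns transfusion. The interval that it closes is not censored, because that interval was not ongoing at the cutoff. If that interval is the patient's longest, its end enters the Kaplan-Meier analysis as an event.

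**3. Illustration of size (every parameter assumed)**

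Hemoglobin moves toward B + A on drug and back toward B on hold. The drug effect is constant over 260 weeks, with visits every 3 weeks on drug. Dose titration and the one-level reduction after a rise of 2 g/dL or more were not modelled. The table gives the median longest interval in weeks among simulated responders (half-life 6 weeks, measurement SD 0.2 g/dL, hold visits every 3 weeks, 300 runs per cell).

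| B | A = 2 | A = 3 | A = 5 |
|---|---|---|---|
| 9.9 | 33 | 12 | 9 |
| 9.6 | 129 | 15 | 9 |
| 9.4 | 237 | 33 | 21 |
| 9.0 | 240 | 111 | 90 |
| 8.5 | 237 | 249 | 252 |
| 7.5 | 240 | 252 | 252 |

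In the A = 2 column every plateau lies below 12 (for example 9.6 + 2 = 11.6), so holds there are triggered only by the assumed measurement noise.

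Eight settings were run: half-life 3 or 6 weeks, SD 0.2 or 0.4, hold visits every 1 or 3 weeks.
- B = 9.6 and 9.9: duration fell or stayed level as A rose, apart from a few cells with few responders.
- B = 9.0, A = 3: strongly dependent on assumptions, for example 45 weeks (half-life 3, SD 0.4, visits every 3 weeks) and 248 weeks (half-life 6, SD 0.2, weekly visits).
- B = 8.5, A = 5: from 66 to 255 weeks.
- B = 7.5: holds never shortened it materially.

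Cumulative duration was checked at B = 9.5 (SD 0.3, half-life 3 or 6 weeks, hold visits every 1 or 3 weeks), counting only periods of 8 weeks or more. Ranges of medians, in weeks:

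| A | Longest interval | Cumulative duration |
|---|---|---|
| 2.5 | 21–29 | 123–181 |
| 3.0 | 11–18 | 42–152 |
| 3.5 | 9–15 | 9–116 |

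Without holds both measures were about 249–255 weeks.

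**The case against.** The strongest reply is that the SAP already covers much of this. It summarizes the number of episodes and cumulative duration, a mean-value version of HI-E beside the one worded "All hemoglobin values increase of" (SAP 5.8.2.3), the maximum mean hemoglobin change (SAP 5.8.2.10), and dose delays (SAP 5.6). Time actually spent above threshold under the whole regimen, holds included, is also a legitimate quantity. The endpoint is secondary, all summaries are descriptive, and the primary objective is safety.

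Much of that stands. It is why the current rule should stay and why this is not a critical defect. The cumulative summary is only a partial cure: sub-threshold time on hold is still lost, and short periods appear not to count because the SAP describes the repeated periods as lasting at least 8 weeks.

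A reader might infer four stronger things that the documents do not support:
- *The strongest responders are penalized, so duration generally shortens as response grows.* The driver is a high baseline together with reaching 12. A patient rising from 7.5 to 12 (+4.5) is still +3.5 at 11, while one rising from 9.9 to 12 (+2.1) must lose response. The inverse pattern belongs to higher-baseline patients only.
- *Kaplan-Meier counts every hold as a failure.* Only the longest interval enters the main duration analysis, so a patient contributes at most one event.
- *Every such patient who reaches 12 is truncated.* The value must occur on a dosing day and the hold must be completed. A response ongoing at cutoff is censored, and a late hold may leave the longest interval long.
- *The administrative gaps in Protocol 10.10 do the same.* They are not triggered by hemoglobin, are limited to two points in treatment and need discussion with the sponsor. The threshold argument does not reach them.

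**Conclusion.** The point holds in a bounded form. For LTB patients with baseline of 9.5 g/dL or more, a completed hold under Protocol 10.8 necessarily produces a value below baseline + 1.5 g/dL, and SAP 5.8.2.5 closes the interval there. That follows from the documents' own thresholds and needs no modelling. At baselines of about 9.0 to 9.5 g/dL it is likely, but rests on assumed hemoglobin kinetics, measurement noise and visit spacing. At 8.5 g/dL or below it is usually small, although at 8.5 itself some settings showed a clear effect.

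Within higher-baseline LTB patients, the longest-interval duration and part of the cumulative duration are biased downward as measures of how long drug effect lasts. The simulated weeks show the mechanism and do not forecast the trial's result. The overall bias cannot be sized: the share of LTB patients at 9.5 or above, the number who reach 12 and the A536-03 entry limit are all absent. SAP 4.1 also pools A536-03 data for patients who rolled over directly, and the hold rule of that study is not reproduced.

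This should be fixed before database lock. As a descriptive secondary endpoint, it does not threaten the study's primary conclusions.

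**What to change.** Leave the dosing rule, the current duration rule and the HI-E responder definition in SAP 5.8.2.3 as they are. Add to SAP 5.8.2.5:

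1. **A pre-specified sensitivity analysis of LTB duration.** Sub-threshold values from the start of a hold for hemoglobin of 12 g/dL or more, up to the second scheduled visit after dosing resumes, do not end the interval if hemoglobin is again at least baseline + 1.5 g/dL by that visit. Otherwise the interval ends at the first sub-threshold value.
2. **Two presentations of that duration,** with and without the sub-threshold hold time counted, so that bridging a hold does not silently credit time below threshold.
3. **A count of LTB response ends that fell within a hold,** overall and by baseline hemoglobin (below 9.5; 9.5 or more).

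The recovery condition limits how far a hold can be bridged. Leaving 5.8.2.3 alone means that no 8-week responder is created by joining values across a hold.

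The cost is a paragraph of SAP text and one extra derivation from dosing dates and hemoglobin values already collected. The downside is a second duration figure to explain in the study report.
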